#### **2.A.3.f.3a. ESBR-m Session 1 – Dementia: what does it mean for me and my family?**

Session 1 objectives are to:

- increase caregiver knowledge about dementia (~20 minutes)
- build caregiving skills (tailored to the needs of each small group) (~40 minutes)
- emphasize the importance of self-care (stress awareness) (~15 minutes)
- introduce the relaxation technique of guided imagery (~15 minutes)

Session 1 is designed to increase the caregiver's knowledge of dementia, its causes, and how disease impacts the brain to create symptoms of dementia. It simplifies the most common causes of dementia into relatable, understandable information (information is adapted to the needs of each group based on care receiver

diagnosis). This session explains common symptoms of dementia syndromes using concrete examples provided both by the leader of the session and caregiver participants.

Targeted skill-building to address care recipient symptoms (and other stressors) elicited from participants is integrated into the session to maximize training in skills pertinent to the group. Discussion is focused around challenging symptoms of dementia experienced by participants and skills to address these symptoms are interwoven into the discussion. Information and skill sheets that focus on specific symptoms and behaviors are prepackaged on the caregiver tablets for easy access.

Caregiver self-care is emphasized through group discussion of the following: stress warning signs, identification of specific stressors, and introduce appropriate use of problem-focused and emotion-focused coping for controllable and uncontrollable aspects of stressors.

The relaxation technique covered in Session 1 is guided imagery, including instruction and practice. Guided imagery audio-visual exercises will be prepackaged on the caregiver tablets. Continued use is encouraged; participants set self-made goals for implementation.

### **2.A.3.f.3b. ESBR-m Session 2 – Dementia: what resources are available to help me and my family?**

Session 2 objectives are to:

- increase caregiver knowledge of dementia resources (~30 minutes)
- build caregiving skills (tailored to the needs of each small group) (~30 minutes)
- emphasize the importance of self-care (sleep hygiene) (~15 minutes)
- introduce the relaxation technique of deep breathing (~15 minutes)

Session 2 is designed to increase the caregiver's knowledge of resources available within VA, the local community, and on a national level. Participants' prior use of dementia resources is discussed and education is provided regarding additional available resources. Resources that are available 24/7 are highlighted (e.g., Veterans Crisis Line; VA Caregiver Support Line). Medical and mental health services are explained (e.g., primary care, psychiatry, neurology), other consultation services are identified (e.g., driver evaluation, respite care), and specialty centers are introduced (e.g., GRECC, PADRECC, academic medical centers). National organizations with missions dedicated to causes of dementia and caregivers are introduced and their services (e.g., support groups) are discussed. Contact information and access to all resources is facilitated through tablet customization. Information is adapted to the needs of each group based on care receiver diagnosis.

Targeted skill-building to address care recipient symptoms (and other stressors) elicited from participants is integrated into the session to maximize training in skills pertinent to the group. Discussion is focused around challenging symptoms skills to address these symptoms are interwoven into the discussion.

Self-care activities from the previous session are briefly discussed and continued self-care is emphasized. Sleep hygiene education and discussion is included due to the fluctuations in sleep (Carter, 2003) most likely due to the demands of care provision and sleep problems (Carter & Chang, 2000; Wilcox & King, 1999) in caregivers. Exercise commensurate with physician approval is also promoted due to its effects on sleep (King, Baumann, O'Sullivan, Wilcox, & Castro, 2002) in addition to its general paucity in caregivers (King & Brassington, 1997).

The relaxation technique covered in Session 2 is deep breathing, including instruction and practice sessions. Continued use (instructional materials prepackaged on caregiver tablets) is encouraged with participants setting self-made goals for implementation.

### **2.A.3.f.3c. ESBR-m Session 3 – Dementia: How can I best communicate with my sources of support?**

Session 3 objectives are to:

- build caregiver communication skills (~50 minutes)
- emphasize the importance of self-care (planned pleasant activities) (~20 minutes)
- introduce the relaxation technique of progressive muscle relaxation (~20 minutes)

Session 3 is designed to enhance the caregiver's ability to communicate with family, friends, and health care providers. Targeted skill-building geared toward effective communication is the focus of this session. Role play is utilized to promote effective communication techniques. Skill-building targeted at improving caregiver/health care provider communication is modeled after the National Institute on Aging publication *Talking with your doctor: a guide for older people* (copies prepackaged on caregiver tablets). Communication tools, preparing for a healthcare appointment, getting information from healthcare providers, and partnering with healthcare providers to make decisions are addressed in detail.

Self-care activities from the previous sessions are briefly discussed and continued self-care is emphasized. This session will specifically focus on planning pleasurable activities.

The relaxation technique covered in Session 3 is progressive muscle relaxation, including instruction and practice sessions. Continued use (instructional materials and audiovisual segments are prepackaged on caregiver tablets) is encouraged with participants setting self-made goals for implementation.

#### **2.A.3.f.3d. ESBR-m Session 4 – Dementia: How can I cope with the stress caused by dementia?**

Session 4 objectives are to:

- build caregiver coping skills (~45 minutes)
- solidify the importance of self-care (review) (~15 minutes)
- review of learned relaxation techniques (~30 minutes)

Session 4 is designed to improve the caregiver's coping skills, specifically targeted to address the challenges of being a dementia caregiver. Ways to manage common symptoms of dementia syndromes using concrete examples, provided both by the leader of the session and caregiver participants, are demonstrated and practiced in role play. The intervention leader will aid participants in reframing cognitive, behavioral, and psychiatric symptoms of dementia as manifestations of damage to the brain.

Targeted skill-building to address care recipient symptoms elicited from participants is integrated into the session to maximize training in skills pertinent to the group. Non-pharmacological interventions for dementia symptom management from previous sessions are reviewed and consolidated.

Self-care activities from the previous sessions are discussed; importance of continued self-care is solidified.

The relaxation techniques covered in Sessions 1-3 are reviewed and consolidated. Continued use post-intervention is encouraged with participants setting ongoing goals for implementation.

**2.A.3.f.3e. ESBR-m Booster Session.** The 90-minute booster session (1-month after the final intervention session) is designed to briefly review dementia knowledge and resources available to dementia patients and their caregivers. Caregiving skills, as they pertain to current stressors, are honed in a manner that is tailored to the small group's needs. The importance of continued self-care is accentuated. Intervention relaxation techniques are revisited and continued use is fostered.

**2.A.3.f.4. Usual Care (plus supplemental educational materials).** Participants randomized to the Usual Care (UC) group will receive supplemental educational materials (e.g., VA Caregiver Support Program; Veterans Crisis Line; National Institute on Aging's "Understanding Memory Loss").

**2.A.3.f.5. Follow-up (at 3-months post-intervention).** Trained study staff, blind to the participants' ESBR-m/UC assignment, will administer follow-up assessments 3 months after the conclusion of the intervention or assignment to usual care. These assessments will mainly occur over the telephone. Packets with assessment aids will be sent to the caregiver prior to each assessment. Should caregivers prefer, in-person assessments will also be offered.

**2.A.3.f.6. Study Conclusion.** Similar to referral procedures implemented throughout the study, at the conclusion of the study all participants will be provided with referrals for services for significant stress, mental health challenges, or cognitive concerns.

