experience. For example, we will send out thank you cards to all participants and will make follow-up telephone calls to express gratitude for participation. We will follow procedures that we have successfully used in our previous research.

**2.A.3.e. Screening Procedures.** Participant screening for eligibility and other data collection will mainly occur during telephone interviews. Should caregivers prefer, face-to-face (in-person) screening/assessment will also be offered. An interview will be conducted with caregivers to determine study eligibility. During this interview, study staff will explain the study, its requirements, and answer any questions the potential participant may have. Upon the potential participant's willingness to be screened, study staff will ensure all inclusion criteria are met and screen the potential participant for all exclusionary criteria. The results of all screening assessments will be reviewed by the PI in consultation with Co-I's. After consensus determination of study eligibility, the Study Coordinator will contact the participant to schedule a Baseline assessment (if eligible), or provide appropriate referral (e.g., VA Caregiver Support Program) and explanation (if not deemed eligible). Both "screen failures" and eligible participants who drop out prior to receiving any intervention will be replaced.

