### **2.A.3.f. Procedures Involving Eligible Participants**

#### **2.A.3.f.1. Enrollment, Randomization, and Baseline Assessment**

Enrollment and Randomization. Once participants are deemed eligible, they will be invited by the Study Coordinator to participate in the study, if willing and able to provide informed consent. At this point, the Data Manager will randomize the participant to one of two arms: ESBR-m or UC. For randomization, a modification of the Efron procedure (Efron, 1971) developed by [name] (Kraemer, 1981) will be implemented to assure the two groups are comparable at baseline in terms of dementia subtype. Participants who drop out after receiving any intervention will not be replaced, but their data will be used in mixed-effects analyses.

Baseline Assessment. Trained study staff, blind to the participants' ESBR-m/UC assignment, will administer a baseline assessment including clinicodemographics and measures of caregiver burden, depression, and perceived stress, in addition to care recipient functional status (see Section 2.A.3.g. for a description of outcome measures). Assessment will mainly occur over the telephone to reduce study participation burden. Packets with assessment aids will be sent to the caregiver prior to each assessment. Should caregivers prefer, in-person assessments will also be offered.

Mental Health referrals to Stanford Outpatient Psychiatry Clinics will be offered to all participants who score 16+ on the CES-D, in addition to participants who endorse symptoms of significant clinical concern, as determined by study staff. All participants are also provided information on accessing the VA Caregiver Support Program and the Veterans Crisis Line.

**2.A.3.f.2. Mobile Media Education and Skill-Building Rehabilitation Intervention (ESBR-m).** Our ESBR-m intervention consists of four, 90-minute group ( $\leq 5$  participants) sessions. **These four sessions are supplemented with a booster session one month following the last intervention session.**

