Title: Mobile Tablet Education to Advance Caregiver Health

NCT #: NCT03417219

March 3, 2014

**2.A.3.g. Study Measures.** *Zarit Burden Interview (ZBI)* [1]. Several versions of the ZBI have been used successfully as outcome measures in interventions for dementia caregivers [2, 3]. *Center for Epidemiological Studies-Depression (CES-D)* [4]. The CES-D is frequently used to assess depression in dementia caregivers and has been shown to be sensitive to changes in caregiver depression post intervention [5]. *Perceived Stress Scale (PSS)* [6]. The PSS has been used successfully to measure perceived stress in dementia caregivers [7]. *Global Deterioration Scale (GDS)* [8]. The GDS is a semi-structured rating of functional status in degenerative dementia. It has been successfully used in prior studies of dementia caregiver intervention with adequate reliability [9]. *Telephone Cognitive Screen (T-CogS)* [10]. The T-CogS is a brief mental status examination designed to be administered over the telephone. Scores on the T-CogS strongly correlate with MMSE scores ( $r = 0.88$ ,  $p < 0.001$ ) [11]. An exclusion cutoff score of  $< 20$  on the T-CogS is chosen to match a MMSE cutoff of  $< 23$  [12]. *Caregiver Interview*. All caregivers will also be administered a structured interview to ascertain information on levels of socialization and pleasurable activity participation.

**2.A.3.h. Data Management.** Integrity of data collection, scoring, and entry/verification will be overseen by the MIRECC Data Analyst/Database Manager and the PI.

**2.A.3.i. Statistical Analyses.** While the proposed project is designed to assess study feasibility, to test the hypotheses outlined in the Specific Aims (Section 2) we will use mixed-effects modeling to fully utilize outcome data measured over time (baseline and follow-up assessments) and to better handle missing outcome information in line with the intention to treat principle. [name] will serve as a statistical consultant, given her expertise in clinical trial and mixed modeling methodologies.

1. Zarit, S., *The hidden victims of Alzheimer's disease: Families under stress*. 1985: NYU Press.

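### As worded, follow-up appears to be timed from the end of the intervention in ESBR-m but from assignment in UC, so arm is confounded with elapsed time; the effect is probably small and cheap to avoid

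*Protocol*

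**What the plan says.** **Follow-up.** Protocol section 2.A.3.f.5 describes one follow-up, headed as 3 months post-intervention, at which staff "will administer follow-up assessments 3 months after the conclusion of the intervention or assignment to usual care".

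**Assignment and baseline.** Section 2.A.3.f.1 randomises once eligibility and consent are settled: "At this point, the Data Manager will randomize the participant to one of two arms: ESBR-m or UC". The baseline assessment is described after that step. Section 2.A.3.e says that after the eligibility decision "the Study Coordinator will contact the participant to schedule a Baseline assessment (if eligible"). Neither section dates baseline relative to session 1.

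**Intervention.** Section 2.A.3.f.2 states: "Our ESBR-m intervention consists of four, 90-minute group" sessions, with at most 5 participants per group, "supplemented with a booster session one month following the last intervention session". The spacing of the four sessions is not given. Section 2.A.3.f.4 defines UC by the educational materials supplied, with no period that ends.

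**Analysis.** SAP section 2.A.3.i plans mixed-effects models of "outcome data measured over time (baseline and follow-up assessments"). It does not say whether time enters as visit or as elapsed time.

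**The concern.** Randomisation makes the arms comparable at assignment. A comparison at follow-up is clean only if both arms are then observed over the same interval. Here the rule itself appears to set different intervals. Caregiver burden, depression and stress, and the care recipient's functional rating, may all change over weeks without any treatment effect. If follow-up is coded as one visit, the arm-by-time term estimates the treatment effect plus whatever drift falls in the extra ESBR-m time. A mixed model does not remove this by itself.

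The between-arm contrast is meant to be used. The SAP says "While the proposed project is designed to assess study feasibility, to test the hypotheses outlined in the Specific Aims" it will fit these models, and Protocol section 2.A.3.a says the results will establish efficacy.

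**Working it through.** The documents give no figure to reproduce: they state no power calculation, drift rate or alpha. The check is timing arithmetic, followed by an illustration on stated assumptions.

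**1. Elapsed time from assignment**

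- UC: 3 months.
- ESBR-m: wait for a group + course length + 3 months.
- Difference: wait + course length, which is above zero for any course that takes time.

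The course length is 3 × the session spacing. Spacing is an assumption (weekly or two-weekly). Take session 4 as the end of the intervention, no wait, and a month of 30.44 days:

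- weekly: 21 / 30.44 = 0.69 month, so ESBR-m is seen at about 3.7 months;
- two-weekly: 42 / 30.44 = 1.38 months, so about 4.4 months.

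Twenty ESBR-m participants in groups of at most 5 need at least 20 / 5 = 4 groups, so some wait is plausible. Its length is not stated.

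**2. Elapsed time from baseline**

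The model runs from baseline, not from assignment. The course-length difference carries over if baseline is dated alike in both arms and before session 1. The wait carries over only if baseline precedes it. Scheduling baseline once eligibility is decided points that way but does not settle it.

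**3. Bias = gap × drift**

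The drift of 0.02, 0.05 or 0.10 SD per month is assumed.

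| Spacing | 0.02 | 0.05 | 0.10 |
|---|---|---|---|
| Weekly (0.69 month) | 0.014 | 0.034 | 0.069 |
| Two-weekly (1.38 months) | 0.028 | 0.069 | 0.138 |

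Each month of wait between baseline and session 1 would add 0.02 to 0.10 SD.

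**4. Standard error**

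Inputs are 20 per arm (Protocol section 2.A.3.a) and an assumed baseline-to-follow-up correlation of 0.6.

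- Change score: √(2 × 2 × (1 − 0.6) / 20) = 0.283 SD.
- Baseline-adjusted: √(2 × (1 − 0.36) / 20) = 0.253 SD.

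**5. Type I error**

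With an assumed two-sided alpha of 0.05 and k = bias / SE, the error is Φ(−1.96 + k) + Φ(−1.96 − k). Change score / baseline-adjusted:

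| Spacing | 0.02 | 0.05 | 0.10 |
|---|---|---|---|
| Weekly | 0.050 / 0.050 | 0.052 / 0.052 | 0.057 / 0.059 |
| Two-weekly | 0.051 / 0.051 | 0.057 / 0.059 | 0.078 / 0.085 |

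**6. Correcting by model instead (illustrative only)**

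Suppose drift is linear and the UC interval from baseline is exactly 3 months, which the documents do not establish. The correction scales the UC change by r = (3 + gap) / 3, which is 1.23 or 1.46. The change-score SE becomes √(0.04 × (1 + r²)), where 0.04 = 2 × (1 − 0.6) / 20. That is 0.317 or 0.354, against 0.283 uncorrected. A modelled correction costs precision; aligned scheduling does not.

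**The case against.** **The sentence is elliptical.** Its heading gives both arms one label, 3 months post-intervention, and the wording could mean the conclusion of either condition. This stands as a reason to say that follow-up appears to be split. It does not rescue the text: UC has no defined end, so that reading yields no date.

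**The effect is small and conditional.** With weekly sessions, type I error is at most 0.059. The 0.085 needs both two-weekly sessions and the top of the drift range; with a t reference on 38 degrees of freedom it is 0.083. Caregivers are selected on distress, so regression to the mean may fall mostly early and leave little drift in the extra weeks. Positive clustering within ESBR-m groups would enlarge the true SE and make this bias relatively smaller. The harm also depends on coding time as visit, which the SAP does not say. All of this stands, and it keeps the point minor.

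**A reader might infer a wider gap because the booster belongs to the intervention.** That would add a month. The text leans against it: the booster is timed from the last intervention session, and Session 4 already speaks of the period afterwards ("Continued use post-intervention is encouraged with participants setting ongoing goals for implementation"). The figures here therefore use session 4.

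**Conclusion.** The point holds as a minor design weakness. Following section 2.A.3.f.5 on its natural reading, ESBR-m is assessed later from assignment by at least the course length, and nothing in either document aligns the arms. The timing difference follows from the text; its length does not, because session spacing and wait are unstated.

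The illustrated bias is 0.01 to 0.07 SD (weekly) or 0.03 to 0.14 SD (two-weekly), against an SE of 0.25 to 0.28 SD. These sizes rest on assumed spacing, linear drift, correlation and alpha, with no wait and session 4 as the anchor.

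A reader might infer that the comparison is materially biased, or biased in favour of one arm. The documents do not support that: they give no drift rate or direction, and the plausible range lies mostly near the nominal error rate. Nor do they support a firm figure for the precision lost by correcting in the model, since the UC interval from baseline is not fixed. The SAP's feasibility framing further limits the consequence, although hypothesis tests are planned.

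**What to change.** 1. Keep the ESBR-m assessment at 3 months post-intervention. Schedule the single UC visit at the same planned interval from baseline, using the follow-up window of the concurrent ESBR-m group. Where no group is forming, including after the last group has started, use a fixed offset equal to the planned wait plus course length plus 3 months. Date baseline the same way in both arms.
2. Record the days from baseline to follow-up and report them by arm.
3. Add to the SAP a sensitivity mixed model using actual time since baseline with an arm-by-post term. Note that it relies on linear drift and loses precision.

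**Cost.** Wording in both documents and rescheduling of one existing visit. With session 4 as the anchor and no wait, UC visits move about 0.7 month (weekly) or 1.4 months (two-weekly) later, plus any planned wait. The downside is slightly more time for UC dropout. No visits are added, and randomisation and intervention are unchanged.

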Title: Mobile Tablet Education to Advance Caregiver Health

NCT #: NCT03417219

March 3, 2014

**2.A.3.g. Study Measures.** *Zarit Burden Interview (ZBI)* [1]. Several versions of the ZBI have been used successfully as outcome measures in interventions for dementia caregivers [2, 3]. *Center for Epidemiological Studies-Depression (CES-D)* [4]. The CES-D is frequently used to assess depression in dementia caregivers and has been shown to be sensitive to changes in caregiver depression post intervention [5]. *Perceived Stress Scale (PSS)* [6]. The PSS has been used successfully to measure perceived stress in dementia caregivers [7]. *Global Deterioration Scale (GDS)* [8]. The GDS is a semi-structured rating of functional status in degenerative dementia. It has been successfully used in prior studies of dementia caregiver intervention with adequate reliability [9]. *Telephone Cognitive Screen (T-CogS)* [10]. The T-CogS is a brief mental status examination designed to be administered over the telephone. Scores on the T-CogS strongly correlate with MMSE scores ( $r = 0.88$ ,  $p < 0.001$ ) [11]. An exclusion cutoff score of  $< 20$  on the T-CogS is chosen to match a MMSE cutoff of  $< 23$  [12]. *Caregiver Interview*. All caregivers will also be administered a structured interview to ascertain information on levels of socialization and pleasurable activity participation.

**2.A.3.h. Data Management.** Integrity of data collection, scoring, and entry/verification will be overseen by the MIRECC Data Analyst/Database Manager and the PI.

**2.A.3.i. Statistical Analyses.** While the proposed project is designed to assess study feasibility, to test the hypotheses outlined in the Specific Aims (Section 2) we will use mixed-effects modeling to fully utilize outcome data measured over time (baseline and follow-up assessments) and to better handle missing outcome information in line with the intention to treat principle. [name] will serve as a statistical consultant, given her expertise in clinical trial and mixed modeling methodologies.

1. Zarit, S., *The hidden victims of Alzheimer's disease: Families under stress*. 1985: NYU Press.

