## Study Protocol

### **2.A.3. Research Design and Methods.**

**2.A.3.a. Approach.** To test the feasibility of a group-based education and skill-building rehabilitation (ESBR) intervention in improving dementia caregiver and care recipient outcomes, our proposed trial will consist of 40 family caregivers coping with all-cause dementia who will be randomized to ESBR. Twenty participants will be randomized to receive mobile media ESBR (ESBR-m), and 20 participants will be randomized to receive usual care plus supplemental educational materials on dementia (UC).

The results of this project will determine the efficacy of a low-cost, pragmatic intervention for caregivers of Veterans with all-cause dementia and will be used to build upon prior findings indicating the efficacy of resource-intensive methods to rehabilitate caregivers of Veterans with all-cause dementia.

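### Feasibility is a stated purpose, but the measures and analysis sections define no feasibility outcome, and replaced non-starters can drop out of uptake and retention figures

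*SAP*

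**What the plan says.** **Purpose.** Protocol 2.A.3.a gives the aim as "To test the feasibility of a group-based education and skill-building rehabilitation (ESBR) intervention in improving dementia caregiver and care recipient outcomes". The same section adds: "The results of this project will determine the efficacy of a low-cost, pragmatic intervention". SAP 2.A.3.i begins "While the proposed project is designed to assess study feasibility" and then turns to hypothesis testing.

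**Size.** "Twenty participants will be randomized to receive mobile media ESBR (ESBR-m), and 20 participants will be randomized to receive usual care" (Protocol 2.A.3.a). No power, precision or dropout assumption is given.

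**Measures.** SAP 2.A.3.g lists the Zarit Burden Interview, CES-D, Perceived Stress Scale, Global Deterioration Scale, the T-CogS (used for exclusion) and a caregiver interview. Of the interview it says: "All caregivers will also be administered a structured interview to ascertain information on levels of socialization and pleasurable activity participation".

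**Analysis.** The only method in SAP 2.A.3.i is this: "to test the hypotheses outlined in the Specific Aims (Section 2) we will use mixed-effects modeling to fully utilize outcome data measured over time". The section also invokes the intention-to-treat principle.

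**Dropouts.** Under Protocol 2.A.3.e, screen failures are replaced, and so are others: "eligible participants who drop out prior to receiving any intervention will be replaced". Protocol 2.A.3.f.1 places randomisation at enrolment. It also says that people who leave after some intervention are not replaced and that their data enter the mixed models.

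**The concern.** A feasibility trial should end with estimates of whether people can be recruited, whether they start and attend, and whether they stay to follow-up. The two sections where those quantities would normally be defined are present and contain none. Recruitment and retention appear in Protocol 2.A.3.c and 2.A.3.d only as procedures and an expectation of success. Sections 2.A.3.f.2 to 2.A.3.f.3e describe four sessions and a booster without an attendance outcome.

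The replacement rule adds to this. Someone can be randomised, never start, and be replaced. If uptake or retention is later computed on the final 40, that person is not counted, and non-starting is one of the things a feasibility trial should reveal. The same person may also be missing from the intention-to-treat set. The documents do not say what counts as having received any intervention in the usual care arm, so the rule may act differently in the two arms.

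At stake is whether the trial can report a pre-defined feasibility result, on a denominator fixed in advance, to support a decision on a larger study.

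**Working it through.** **1. The plan's own figure.** The total is 20 + 20 = 40. No alpha, power, effect size, SD or precision target is given, so the figure cannot be derived from inputs. It is taken as fixed below.

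**2. Feasibility quantities against the text.**

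| Quantity | Measure in SAP 2.A.3.g | Analysis in SAP 2.A.3.i |
|---|---|---|
| Enrolled among eligible approached | none | none |
| Started ESBR-m | none | none |
| Sessions and booster attended | none | none |
| 3-month assessment completed | none | none |
| Burden, depression, stress, care recipient function | yes | mixed model |

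**3. Effect of replacement on uptake (numbers assumed).** The exact (Clopper-Pearson) 95% interval for x out of n has lower limit Beta⁻¹(0.025; x, n − x + 1) and upper limit Beta⁻¹(0.975; x + 1, n − x). The upper limit is 1 when x = n. Suppose 4 people assigned to ESBR-m never start and are replaced, and 20 others start.

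- Final 20 as denominator: 20/20 = 100%, interval 83.2% to 100%.
- Everyone assigned to ESBR-m: 20/(20 + 4) = 20/24 = 83.3%, interval 62.6% to 95.3%.

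**4. Effect on retention (numbers assumed).** Let r be the randomised people replaced, none of them followed up, and L the later losses, which are not replaced. Retention on the final 40 is (40 − L)/40. On all randomised it is (40 − L)/(40 + r).

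| r | L | On final 40 | On all randomised (exact 95% CI) | Difference |
|---|---|---|---|---|
| 4 | 4 | 36/40 = 90.0% | 36/44 = 81.8% (67.3% to 91.8%) | 8.2 points |
| 8 | 4 | 36/40 = 90.0% | 36/48 = 75.0% (60.4% to 86.4%) | 15.0 points |
| 10 | 0 | 40/40 = 100% | 40/50 = 80.0% (66.3% to 90.0%) | 20.0 points |

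For r from 4 to 10 and L from 0 to 8, the difference runs from 7 points (r = 4, L = 8: 80.0% against 32/44 = 72.7%) to 20 points. With r = 0 it is nil. Later losses L appear in both versions.

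**5. Precision available for feasibility estimates.** 16/20 = 80% (56.3% to 94.3%). 32/40 = 80% (64.4% to 90.9%).

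**6. Can the scale comparisons carry the conclusion instead?** With 20 per arm, two-sided alpha 0.05 (assumed), no dropout and no baseline adjustment, a t-test has power of about 15%, 34% and 69% for true differences of 0.3, 0.5 and 0.8 SD. The difference detectable with 80% power is 0.91 SD. With baseline adjustment (normal approximation, assumed correlation ρ) it is (1.96 + 0.84) × √[(2/20)(1 − ρ²)], which is 0.77 SD at ρ = 0.5 and 0.63 SD at ρ = 0.7. Only fairly large effects could be shown reliably.

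**The case against.** **The plan does address its question.** Protocol 2.A.3.a speaks of feasibility in improving outcomes and of determining efficacy, and the scales measure those outcomes. A reader might infer that the plan cannot answer its own question at all. The documents do not support that, because it holds only if feasibility means deliverability alone. What stands is that the purpose is stated inconsistently. SAP 2.A.3.i also sets feasibility apart from the hypotheses and then provides only for the hypotheses.

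**The Specific Aims are unseen.** They may contain feasibility targets, so it cannot be said that none exist anywhere. Nor does SAP 2.A.3.i say that nothing beyond the mixed models will be reported. Even so, an aim stated elsewhere would have no variable in 2.A.3.g and no estimate in 2.A.3.i.

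**Replacement does not itself bias anything.** This is correct. The rule refills the sample and does not remove anyone from a denominator. Later losses are not replaced, and intention to treat is invoked. A reader might infer that uptake and retention will be inflated. The text supports only that they can be, because no denominator is stated. Nor does replacement flatter recruitment, since it means approaching more people over a longer time. How many randomised people the rule would reach is unknown.

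**Pilots need no numerical threshold.** This stands. The interval for 16/20, 56% to 94%, is too wide to separate neighbouring go/no-go bands. A single cut-off can still inform: a rule of at least 16 of 20 passes with probability 5.1% at a true rate of 60% and 83.0% at 85% (assumed rates). Whether to use one is a choice, and its absence is not an error.

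**Conclusion.** The point holds in a limited form. Feasibility is a stated purpose, and the listed measures and analysis contain no feasibility outcome or estimate. That is the main defect, and it rests on sections that are present in full. Replacement is an aggravating factor: randomised non-starters can be lost from uptake and retention figures, and possibly from the intention-to-treat set.

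The size depends on how many randomised people are replaced, which the documents cannot tell us. Four ESBR-m non-starters would move reported uptake by 17 points (100% against 83%). None would move it by nothing. The exact intervals treat the denominator as fixed, which is an approximation if recruitment continues until a set number have started. The power figures assume two-sided alpha 0.05 and full follow-up. They show why 20 per arm does not support the Protocol's statement about determining efficacy for small or moderate effects. They do not show that the comparisons are worthless.

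This should be corrected before enrolment. It does not call the design into question.

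**What to change.** **SAP 2.A.3.g.** Add three feasibility outcomes:

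- the number enrolled out of those eligible and approached;
- ESBR-m attendance, as the share attending a stated minimum of the four sessions, with booster attendance reported separately;
- the share completing the 3-month assessment.

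**SAP 2.A.3.i.** Report each as a proportion with an exact 95% CI. For attendance, the denominator is everyone randomised to ESBR-m. For follow-up completion, it is everyone randomised to either arm. Both include people who were later replaced. State that all randomised participants stay in the intention-to-treat analysis. Describe the scale comparisons as preliminary.

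**Protocol 2.A.3.e and 2.A.3.f.1.** Replacement can stay. Log each replacement by arm, by reason and by whether it came before or after randomisation. Say what counts as having received any intervention in the usual care arm.

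**Protocol 2.A.3.a.** Reword the sentence on determining efficacy to match a feasibility trial with preliminary outcome comparisons.

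Progression thresholds are optional. If the sponsor wants them, it sets the values before the first enrolment.

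**Cost.** Mostly wording. The documents mention no screening or attendance log, so a simple record of people approached, enrolled and attending may have to be added. The trade-off is that uptake and retention figures may look less favourable.
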